## G2. Data Analysis

Provide a description of your plan for data analysis. State the types of comparisons you plan (e.g. comparison of means, comparison of proportions, regressions, analysis of variance). Which is the PRIMARY comparison/analysis? How will the analyses proposed relate to the primary purposes of your study?

The primary outcomes are time to granulation, successful granulation at 8 weeks, and number of failures (e.g. amputation, infection, rejection, re-application) within 8 weeks. Mixed models accommodate the longitudinal design; allow for testing differences between groups in patterns over time as well as at specific time points; are consistent with an intention to treat analysis (9), and are valid for data which are missing completely at random or at random (10). Number of failures as well as number of recurrence of ulcers over the 6 month follow-up will be modelled with a generalized linear model using an appropriate count outcome (Poisson, zero-inflated Poisson, negative binomial for overdispersion). Rate ratios comparing intervention arms will be estimated from this model. Appropriate mixed models (linear or generalized linear, for noncontinuous outcomes or logistic regression for binary data) will be used to test the intervention effect for each of the secondary outcomes (e.g. tissue biomechanics, mobility, patient centered outcomes, recurrence of ulcers, etc). A Kaplan-Meier survivorship analysis will be used for estimating time to event for none successful healing probability over time by treatment and the p-value will be calculated using the Log-rank (Mantel-Cox) test. Hazard ratios will be used to indicate the probability of closure at any given point in time for Derma-Cell v. Integra treatment. Univariate logistic regression analyses will be performed to delineate predictive factors of successful granulation at 8 weeks, successful wound healing at 12 weeks, and successful wound healing at 16 weeks. Results will be controlled for potential confounding variables including age, sex, BMI, HbA1c, neuropathy severity, vascular status, frailty, mobility status, and initial wound size. The p-values for weekly % wound area and % wound area reduction through 16 weeks will be calculated using t tests. All p-values, for both the categorical and continuous data, will be calculated using a two-sided alpha of 0.05.

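### Three unordered primary outcomes, with every p-value at 0.05 and an explicit between-arm model for only one of them; weekly wound area is given to t tests although a mixed model is already named

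*Combined protocol and SAP*

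**What the plan says.** The form's question in G2 (Data Analysis) is in the singular: "Which is the PRIMARY comparison/analysis". The reply is "The primary outcomes are time to granulation, successful granulation at 8 weeks, and number of failures (e.g. amputation, infection, rejection, re-application) within 8 weeks". F1 (Design) gives the same three. Neither section ranks them, sets a testing order, requires all three to succeed, or describes an adjustment. G2 closes with "All p-values, for both the categorical and continuous data, will be calculated using a two-sided alpha of 0.05".

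The between-arm methods in G2 are uneven across the three:

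- **Number of failures:** a count model, with "Rate ratios comparing intervention arms will be estimated from this model".
- **Granulation at 8 weeks:** "Univariate logistic regression analyses will be performed to delineate predictive factors of successful granulation at 8 weeks". This is a search for predictors and is not stated as a comparison of arms.
- **Time to granulation:** no test is stated. The Kaplan-Meier and log-rank text concerns healing and closure.

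On wound area, G2 first says "Mixed models accommodate the longitudinal design; allow for testing differences between groups in patterns over time as well as at specific time points", and assigns mixed models to the secondary outcomes. F1 lists weekly speed of healing among those. G2 then says "The p-values for weekly % wound area and % wound area reduction through 16 weeks will be calculated using t tests". It also says "Results will be controlled for potential confounding variables including age, sex, BMI, HbA1c, neuropathy severity, vascular status, frailty, mobility status, and initial wound size".

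F1 selects the pilot category. G1 (Sample Size) hopes to see trends in outcomes other than application time and foresees a possible later randomized trial to validate them.

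**The concern.** With three primary outcomes, no order, and 0.05 for each p-value, a reader of the results cannot tell which one was meant to count. If any of the three can be presented as the primary finding, the effective false-positive rate is above the stated 5%. For two of the three, the analyst would also have to choose the between-arm test after the fact.

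The wound-area t tests raise the same problem on a smaller scale. A difference in one isolated week can look like an effect, and a plain t test makes no use of the baseline wound size that the trial collects. Because a later trial may be planned from these trends, the plan should say beforehand which result is pre-specified and which are exploratory.

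**Working it through.** **The plan's own figure.** G1 gives 17 per group for application time (3 v 5 min, SD 2, two-sided 0.05, power 80%). An exact noncentral-t calculation gives 16.71, rounded up to 17, with power 80.7%. The figure reproduces. But application time is a secondary outcome in F1, so the calculation does not show which of the three primaries is the main one.

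**Three primaries, if each is tested between arms at 0.05.**

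- Independent tests: 1 - 0.95^3 = 1 - 0.857 = 14.3%. The bound under any correlation is 3 x 0.05 = 15%.
- The documents give no correlations, so a range is assumed. With three standard normal statistics of common correlation r and rejection when any |Z| > 1.96:

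| r | 0 | 0.3 | 0.5 | 0.7 | 0.9 |
|---|---|---|---|---|---|
| P(at least one false positive) | 14.3% | 13.6% | 12.5% | 10.9% | 8.4% |

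- The two granulation outcomes should overlap heavily. F2 (Procedure) schedules granulation assessment only at weeks 5, 6, 7 and 8 up to the week-8 endpoint, so time to granulation and granulated by week 8 draw on the same four readings. With that pair correlated 0.8 / 0.9 / 0.95:
  - failures uncorrelated with the pair: 12.4 / 11.7 / 11.1%;
  - failures correlated 0.5 with both: 11.5 / 10.9 / 10.3%.

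That gives about 10-12%, or 10/5 = 2.0 to 12/5 = 2.4 times the nominal rate.

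**Wound-area t tests.** F2 schedules a formal wound assessment after baseline at weeks 2, 4, 8, 10, 12, 14 and 16, which is seven times. A photograph is taken at every visit, so 16 weekly values are possible. Percent area and percent reduction are counted once, since they are complements if both are relative to baseline. Assumptions: no true difference, normal data, correlation rho^|weeks apart|, 17 or 25 per arm, a two-sample t test at each time point, 40,000 simulated trials per setting.

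| Tests | rho = 0.95 | rho = 0.70 |
|---|---|---|
| Seven scheduled assessments | about 15% | about 28% |
| All 16 weeks | about 19% | about 43% |
| Weeks 8, 12 and 16 only | about 10% | about 14% |

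Cutting back to three unadjusted tests still leaves 10-14%. This is why the fix allows only one tested contrast.

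**What one primary saves compared with Holm, like with like.** Assume 80% v 60% granulated by week 8, proportional hazards, and a log-rank test. Power at 0.05 is about 28% at 17 per arm and 38% at 25 per arm. At Holm's first step alpha is 0.05/3 = 0.0167, with critical value 2.394. By normal approximation:

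- 17 per arm: shift = -0.598 + 1.960 = 1.362 (from power 27.5%); 1.362 - 2.394 = -1.032; power about 15%.
- 25 per arm: shift = -0.305 + 1.960 = 1.655; 1.655 - 2.394 = -0.739; power about 23%.

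**The case against.** **This is a pilot.** F1 says so, G1 speaks of trends and a later trial, and Section D expects wound outcomes, including time to granulation, to be comparable. Strict family-wise control is not normally demanded of such a study. If comparability is expected, reading non-significance as equivalence is at least as great a danger as a false difference. This stands, and it lowers the weight of the point. It does not remove it, because G2 still prescribes formal testing at 0.05 and leaves its own question about the primary comparison unanswered.

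**The inflation is conditional.** G2 states no between-arm test for either granulation outcome. A reader might infer that the plan commits to three tests and so to a 14% error rate. The documents do not support that. The firm finding is that the primary comparison and two of its tests are unspecified; the error figure follows only if all three are tested.

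**Wound area is not primary, and the number of t tests is not given.** Both are true. A reader might multiply 16 independent tests to 1 - 0.95^16 = 56%, but weekly readings on the same wound are not independent, and formal assessments number seven. A reader might also infer that G2 contradicts itself, because a t test cannot adjust for initial wound size. The sentence on confounders directly follows the logistic-regression sentence and may not reach wound area, and a percentage of baseline already uses initial size in part. What remains is that a less suitable method is specified beside one that G2 itself says fits the design.

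**Naming one primary will not rescue power.** Correct: 28-38% on the assumed effect is low. The gain is in interpretation.

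**The text is limited.** Section C refers to a protocol attached in section S, which is not part of the text available. The lack of a multiplicity rule is shown for this document only.

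**Conclusion.** The point holds as a low-to-moderate concern about interpretation, and the change should be made. G2 does not name a primary comparison, applies 0.05 throughout, and gives an explicit between-arm model only for failures. If all three primaries are tested between arms, the chance of at least one false positive is 8-14% across assumed equal correlations of 0.9 to 0, with 10-12% the more plausible range given the overlap of the two granulation outcomes. For wound area the corresponding figures are 15-28% (seven assessments) or 19-43% (16 weeks), under assumed AR(1) weekly correlations of 0.95 to 0.70. All of these correlations are assumptions; none is in the documents.

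A reader might go further and conclude that a confirmatory claim fails. The documents do not support that: the trial is labelled a pilot, and validation is left to a possible later trial.

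**What to change.** 1. In F1 and G2, name one primary outcome and its between-arm test at two-sided 0.05. The choice belongs to the investigators; log-rank on time to granulation is one option, since G2 already uses that test for healing. Report the other two as arm differences or ratios with 95% confidence intervals, labelled secondary or exploratory. Holm across all three is an alternative, but at its first step log-rank power on the assumed effect falls from about 28% to 15% at 17 per arm, and from 38% to 23% at 25 per arm.

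2. In G2, replace the weekly wound-area t tests with the mixed model already named, adjusted for baseline wound area. Report arm differences with 95% confidence intervals at weeks 8, 12 and 16. Test at most one contrast, named in advance.

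The cost is a wording amendment to two sections, with no new patients, visits or data. The downside is fewer formal significance claims.

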## Section H: Potential Risks/Discomforts

#### H1. Potential Risks/Discomforts

Describe and assess any potential risks/discomforts; (physical, psychological, social, legal, or other) and assess the likelihood and seriousness of such risks:

The study devices and assessment tools that will be used in the study are non-invasive, safe, non-toxic and do not emit any radiation. However, like any battery-powered system, there is also a minimum risk of device malfunctioning and overheating. We will inform the subject to contact the research staff immediately if they experience overheating or device malfunctioning. In addition, the study devices are not waterproof, and although they use a low powered battery (similar to a cell-phone battery), they should not be submerged in water. We will inform the subjects to remove the device when ever they go swimming or take a shower.

Subjects will not be charged for any damage or loss of the device. We will inform them to contact us immediately. The device may be replaced upon availability.

There is a minimal risk of interference from Zephyr Bioharness in the functionality of pacemaker/ICD devices. Therefore, to avoid any adverse events, it is recommend by the American Heart Associates to avoid the use of this wearable device on subjects with a pacemaker/IDC. There are no hazards or adverse events reported regarding Zephyr Bioharness.

A vibration perception device will be used to monitor progress and diagnose severity of DPN in lower extremities. The vibration range will be from 0-50 Volts. Participants may feel slight discomfort from the vibration. This device is compliant with medical electrical device safety according to IEC 601-1.

#### H2. Data and safety monitoring plan

Do the study activities impart greater than minimal risk to subjects? No

# H3. Coordination of information among sites for multi-site research

Is the BCM Principal Investigator acting as the SPONSOR-INVESTIGATOR for this multi-site research? No or Not Applicable

Is BCM the COORDINATING CENTER for this multi-site research?

No or Not Applicable

#### **Section I: Potential Benefits**

Describe potential benefit(s) to be gained by the individual subject as a result of participating in the planned work.

There may be no direct benefit to the subject by being in this study. What the researchers find out from this study may help other people with deep and/or chronic wounds. This research compares two dermal matrices after being applied to a deep

wound.

Describe potential benefit(s) to society of the planned work.

It is part of a larger prevention initiative to reduce the high number of diabetic amputations

The body of work in this area suggests opportunities for better patient care by comparing two dermal matrices.

Do anticipated benefits outweigh potential risks? Discuss the risk-to-benefit ratio.

Although there some risks involved in this study associated with the procedures involved, they are minimal and the study does provide the possibility of benefit to subjects. Therefore, the benefits outweigh the risks involved.

#### **Section J: Consent Procedures**

#### J1. Waiver of Consent

Will any portion of this research require a waiver of consent and authorization?

Yes

Please describe the portion of the research for which a waiver is required. (Example: chart review to determine subject eligibility)

We will be screening our patient charts for screening and to determine eligibility.

Explain why the research and the use or disclosure of protected health information involves no more than minimal risk (including privacy risks) to the individuals.

The PHI will not be reused or disclosed to (shared with) any other person or entity, except as required by law, for authorized oversight of the research study, or for other research for which the use or disclosure of the PHI would be permitted under the Privacy Rule.

This is a minimal risk study. There is the possibility for loss of confidentiality. However, the PI and his team will employ ample measures to ensure that the data is coded as much as possible and that it is stored under lock and key at all times. Also, electronic data will only be kept on our network password protected computers.

Explain why the waiver will not adversely affect the privacy rights and the welfare of the research subjects.

Patients will receive the same standard of care whether or not they participate in the research. Subjects are patients of the Co-PI in his clinic. So, their participation will not affect the current or future care in the clinic by their physician.

Explain why the research could not practicably be conducted without the waiver and could not practicably be conducted without access to and use of the protected health information.

If we are not allowed to search our patient; s records, we cannot identify and recruit the patients that are eligible for the study. We have to be able to access the patient chart including their medical information from other physicians in order to verify their eligibility for this study.

This research will not affect the subject is care as they are receiving the standard of care.

Describe how an adequate plan exists in order to protect identifiers from improper use and disclosure.

As there is a possibility of a loss of confidentiality in this study, the PI and his team will employ ample measures such as coding as much of the data as possible. In addition all physical information will be kept in locked file cabinets. All electronic data will be stored on our network password protected computers.

Describe how an adequate plan exists in order to destroy identifiers at the earliest opportunity consistent with conduct of the research, unless there is a health or research justification for retaining the identifiers or such retention is otherwise required by law.

We will destroy identifiers at the earliest opportunity consistent with conduct of the research absent a health or research justification for retaining them or a legal requirement to do so. The use or disclosure of PHI involves no more than minimal risk to the individuals and the waiver will not adversely affect the privacy rights and the welfare of the individuals. PHI is not disclosed to any other person or entity except for the authorized oversight of the research study by the PI and the clinical database administrator. The Division uniformly adheres to all patient and patient data security and confidentiality rules and regulations set forth by the College.

Describe how adequate written assurances exist in order to ensure that the PHI will not be reused or disclosed to (shared with) any other person or entity, except as required by law, for authorized oversight of the research study, or for other research for which the use or disclosure of the PHI would be permitted under the Privacy Rule.

The PHI will not be reused or disclosed to (shared with) any other person or entity, except as required by law, for authorized oversight of the research study, or for other research for which the use or disclosure of the PHI would be permitted under the Privacy Rule.

Information from health records such as diagnoses, progress notes, medications, lab or radiology findings, etc.

Yes

Specific information concerning alcohol abuse:

No

Specific information concerning drug abuse:

No

Specific information concerning sickle cell anemia:

No

Specific information concerning HIV:

No

Specific information concerning psychiatry notes:

Νc

Demographic information (name, D.O.B., age, gender, race, etc.):

Yes

Full Social Security #:

No

Partial Social Security # (Last four digits):

Nic

Billing or financial records:

No

Photographs, videotapes, and/or audiotapes of you:

Yes

Other:

No

Will additional pertinent information be provided to subjects after participation?

No

If No, explain why providing subjects additional pertinent information after participation is not appropriate.

If a patient was screened and was not enrolled, they will not receive any study information. Those patients who were enrolled will have access to that information once the study has been completed.

## J1a. Waiver of requirement for written documentation of Consent

Will this research require a waiver of the requirement for written documentation of informed consent?

No

#### J2. Consent Procedures

Who will recruit subjects for this study?

PΙ

PI's staff

Describe how research population will be identified, recruitment procedures, any waiting period between informing the prospective participant and obtaining consent, steps taken to minimize the possibility of coercion or undue influence and consent procedures in detail.

Research Staff will be located at Baylor Clinic and the study sites for several days of the week in order to recruit participants.

Subjects will be recruited from the Co-PI's own practices. We may get some referrals from their colleagues that work in the same clinic. We have included a Waiver of Partial Consent to cover our screening process. The Co-PIs will identify eligible subjects and alert the coordinator. The coordinator will review all the details of the study with the subject and/or their family. If the subject agrees to participate in the study, they will be screened and then enrolled into the study.

Please note that all subjects will be consented before any screening procedures are done.

Spanish speakers will be consented using a full Spanish version of the consent. We are currently waiting for the Spanish ICF to be sent from WIRB. No Spanish speakers will be consented before this consent form has been submitted and approved.

Are foreign language consent forms required for this protocol?

Yes

Which of the following ways will you document informed consent in languages other than English?

A full-length informed consent document

## J3. Privacy and Intrusiveness

Will the research involve observation or intrusion in situations where the subjects would normally have an expectation of privacy?

No

#### J4. Children

Will children be enrolled in the research?

No

#### J5. Neonates

Will non-viable neonates or neonates of uncertain viability be involved in research?

No

# J6. Consent Capacity - Adults who lack capacity

Will Adult subjects who lack the capacity to give informed consent be enrolled in the research?

No

# J7. Prisoners

Will Prisoners be enrolled in the research?

No

# Section K: Research Related Health Information and Confidentiality

Will research data include identifiable subject information?

Yes

Information from health records such as diagnoses, progress notes, medications, lab or radiology findings, etc.

Yes

Specific information concerning alcohol abuse:

Yes

Specific information concerning drug abuse:

Yes

Specific information concerning sickle cell anemia:

No

Specific information concerning HIV:

No

Specific information concerning psychiatry notes:

No

Demographic information (name, D.O.B., age, gender, race, etc.):

Yes

Full Social Security #:

Yes

Partial Social Security # (Last four digits):

Νc

Billing or financial records:

Yes

Photographs, videotapes, and/or audiotapes of you:

Yes

Other:

No

At what institution will the physical research data be kept?

The physical research will be kept in our BCM offices housed in the [name].

How will such physical research data be secured?

Data will be kept in locked file cabinets that only the research team has access to.

At what institution will the electronic research data be kept?

Electronic data will be kept on network computers in our BCM offices, under the password protected server. Address: \\discovery1.ad.bcm.edu\bcm-dept-icamp

Such electronic research data will be secured via BCM IT Services- provided secured network storage of electronic research data (Non-Portable devices only):

Yes

Such electronic research data will be secured via Other:

Νo

Will there be anyone besides the PI, the study staff, the IRB and the sponsor, who will have access to identifiable research data?

Yes, identify the classes of the persons:

Νo

Please describe the methods of transmission of any research data (including PHI, sensitive, and non-sensitive data) to sponsors and/or collaborators.

Transmissions, if any, will only happen via secure emails.

Will you obtain a Certificate of Confidentiality for this study?

No

Please further discuss any potential confidentiality issues related to this study.

NA

